Official Study Title:

Intimate Partner Violence and Fatherhood Intervention in Residential Substance Abuse Treatment

NCT Number: NCT02979262

Date Last Modified: 8/14/2017

IRB approval: 8/27/2018

Project Title

Intimate Partner Violence and Fatherhood Intervention in Residential Substance Abuse Treatment

Study Rationale and Background Information

Substance use and intimate partner violence (IPV) are two severe problems that often co-occur (Centers for Disease Control & Prevention, 2013; Centers for Disease Control, 2012; Shorey, Stuart, & Cornelius, 2011) and can lead to poor parenting behaviors (Gustaffson & Cox, 2012; McMahon, Winkel, & Rounsville, 2008). Current treatments for co-occurring substance abuse and IPV are lacking ([name], 2013). This study will test initial efficacy of a novel intervention for IPV and substance use among fathers in residential substance abuse treatment: Fathers for Change compared to a standard parenting intervention.

Research Hypotheses

This initial pilot will assess the feasibility, acceptability, and intervention signal of Fathers for Change compared to a Parent Education Condition within a residential treatment center for substance dependent men. We will test the following specific hypotheses:

1. Fathers in the Fathers For Change (FFC) group will have comparatively greater completion rates in both the residential and aftercare components of the program compared to fathers in the Dads 'n' Kids (parenting education-PE) program.
2. Fathers in the FFC group will exhibit greater improvement in hostile cognitions, emotion regulation and physiological arousal at the time of residential treatment discharge (12 weeks) and following aftercare sessions (16 weeks) than fathers in the Dads 'n' Kids group.
3. Men in the FFC group will experience comparatively less substance abuse relapse at the 3 month-follow-up than in the Dads 'n' Kids group.
4. Men in the FFC group will report fewer intimate partner violence (IPV) incidents and CM risk behaviors at 24 week follow-up than fathers in the Dads 'n' Kids group.
5. Exploratory Hypothesis: The relationship of Intervention (FFC versus PE) to substance abuse relapse, IPV, and child maltreatment risk behavior (at 24 week follow-up) will be mediated by reductions in hostile cognitions and emotion regulation (measured at 16 weeks).

Study Design

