Sixty fathers, their female co-parent and youngest child will be recruited to participate in the study. At the time of intake at Westcare's Emerge Program and Salvation Army's Residential Substance Abuse Rehabilitation Program, fathers will be provided flyers about the study. Men who express an interest in participating in a parenting program as part of their treatment will fill out an initial interest form with their counselors (including their name, arrival and discharge date, information about how often they're in contact with their children) and have their counselors submit this form to the Project Coordinator. The Project Coordinator will schedule a screening with the potential participant and will be asked to sign a consent form,

and to sign a release of information to review their SA treatment and criminal history. Men will be told that his questionnaire and records will be reviewed and will be contacted further if considered eligible by the PI based on the study's requirements.

This will provide the opportunity to contact the mother to conduct a phone screening in regards to IPV history and willingness to participate. If the mother indicates an IPV history that involved hospitalization or strangulation or a current full no contact protective order, he will be notified that based on the demographic screening, he is not eligible for the study. If the father is eligible and agrees to participate in the study, the research assistant will contact the father to set up a baseline assessment and the co-parent will be contacted to set up a baseline interview by phone or in-person if she wants to participate. If the father is not eligible for the program we will remove the bottom portion of his screening form that includes personal information (name, arrival and discharge date, and WestCare or Salvation Army counselor information) and shred it. The top portion including de-identified information (IPV history and contact with children) will be kept to keep track of the number of referrals compared to the number of participants in the program.

Mothers of the father's youngest child will be recruited in several ways:

1. When she visits the facility she will be approached by study staff in person.
2. She will be mailed study flyers asking her to contact the research office.
3. Westcare or Salvation Army staff will call mothers and ask permission for study staff to contact them to tell them about the study.

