Following completion of baseline assessments, subjects will be randomly assigned to the FFC intervention or the Parenting Education (Dads 'n' Kids) condition. To increase the likelihood that treatment groups are balanced with respect to demographic variables, and moderators, subjects will be assigned to treatment conditions through urn randomization using a Microsoft Access-based program. In urn randomization, an algorithm modifies ongoing randomization probabilities based on prior composition of treatment groups and maximizes multivariate equivalence of groups

Fathers in each treatment group will meet individually with their assigned therapist once per week for 50-60 minutes of treatment. The Fathers for Change Intervention has three phases: individual focused, co-parent relationship focused and restorative parenting focused. Beginning with motivational interviewing, the clinician and father will discuss child development, the impact of SA and violence on parenting, and the father's own childhood experiences of SA and violence and how he would like things to be different for his own children. The clinician will also provide skills training to reduce hostile cognitions and increase emotion regulation skills. In co-parenting focused sessions the clinician will teach communication and problem solving skills, these topics will be addressed with or without the co-parents participation. In family sessions the clinician focuses on restorative parenting to

rebuild the father-child relationship. These phases can be delivered either individually to the father or together with his children present. The decision whether family members are invited to participate will be made on a case by case basis dependent on safety of the co-parent and child, their wish to participate and their ability to come to the treatment facility.

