Official Study Title:

Intimate Partner Violence and Fatherhood Intervention in Residential Substance Abuse Treatment

NCT Number: NCT02979262

Date Last Modified: 3/25/2019

Data analysis Plan

Because the variables of interest involved a mix of continuous, count, dichotomous, and multinomial variables, generalized linear modeling techniques were used to test for between group differences in the demographic and clinical characteristics of the participants, the process outcomes, and the secondary outcomes only measured once or twice at the end of treatment or the end of the 3-month period of follow-up. Similarly, generalized estimating equations (GEE), the repeated-measures extension of generalized linear modeling, was used to test for between group differences in baseline values, within-group change over time, and between-group differences in the rate of change for primary and secondary outcomes measured two to five times from randomization through the 3-month period of follow-up. When there were only two measurements, time was dummy coded to represent the first and second measurements. When there were three or more measurements, time was coded as a continuous variable representing weeks from randomization. Consistent with the CONSORT recommendations, process, primary, secondary, and end-point outcomes were analyzed for both the intention-to-treat and per-protocol samples.

Across statistical analyses, dummy coding was used to represent facility and treatment assignment; and preliminary analysis of descriptive statistics, graphical representation, and goodness of fit statistics were used to determine the appropriate response distribution and link function for use in the final analysis of each dependent variable. When it was not fixed at 1.0, the deviance/df statistic was used to determine the dispersion parameter. Given the limited sample size and the potential costs of a Type II error in this type of pilot study, statistics with p values less than .10 were considered statistically significant. Despite this, there was a focus on the consistency of findings across variables and intention-to-treat versus per-protocol samples.

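### Planned time left in residence can be derived before randomization but is not used, so hypothesis 1 may mix scheduled discharge with drop-out and lose power

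*Protocol*

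**What the plan says.** The protocol's Study Design section has interested men complete a form with their counselors, with details "including their name, arrival and discharge date". Consent, record review and the baseline visit come later, and allocation later still: "Following completion of baseline assessments, subjects will be randomly assigned to the FFC intervention" or to the parent-education comparison. The same section shreds the portion of the screening form holding these dates only for ineligible men, which implies that they are kept for those enrolled.

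Hypothesis 1 (Research Hypotheses) is that FFC fathers "will have comparatively greater completion rates in both the residential and aftercare components of the program" than fathers in the comparison arm. Hypothesis 2 puts residential discharge at 12 weeks, and Study Design puts the post-residential interview at the same time. Sample Size describes men in a 6-month residential treatment.

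The inclusion and exclusion criteria, in Study Design and again under Study Population, set no minimum remaining stay and no limit on time since admission. The urn aims for groups "balanced with respect to demographic variables, and moderators". It lists no variables, and the moderators in Table 1 include neither facility nor time left in residence. The SAP (Data analysis Plan) says that across analyses "dummy coding was used to represent facility and treatment assignment". It does not mention time left.

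**The concern.** How long a man is due to stay when he is randomized is likely to predict whether he is still in residence at week 12. If completion means remaining to week 12, a man due to leave earlier cannot complete in either arm, whatever the treatment does. Such men add the same failures to both arms and shrink the observed difference. Chance differences between arms in their number add noise.

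At stake are the power and the reading of the first hypothesis in a 60-man pilot. The SAP already relaxes its significance level to .10 because the sample is small and a missed effect is costly. Leaving unused a baseline value that the trial already holds works against that aim.

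**Working it through.** **The plan's own figure.** 60 fathers × 3 family members = 180, as stated. The documents give no completion rates, effect size or power, so nothing more can be reproduced. What follows is illustrative.

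**Timeline.** Six months is about 26 weeks, and 26 − 12 = 14. On that stay, a man randomized more than about 14 weeks after arrival is due to leave before week 12, and no criterion prevents this. A man randomized at intake would still be resident at week 16, when aftercare is meant to be over. Either way, stay left bears on hypothesis 1, and the two durations need reconciling.

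**Inputs.** From the documents: 60 men and significance at .10. Assumed: 1:1 allocation (30 per arm), two-sided testing, completion of 80% v 60% among men with enough stay left, and a share q of short-stay men who all count as non-completers.

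**Formula.** Power = Φ(d/SE − 1.645), with SE = √{[p₁(1−p₁) + p₂(1−p₂)]/n}. Under dilution, each rate is multiplied by (1 − q) and n stays at 30. When short-stay men are separated, the rates stay at 0.80 and 0.60 and n becomes 30(1 − q).

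- q = 0: SE = √(0.40/30) = 0.1155; 0.20/0.1155 = 1.732; power 53%.
- q = 0.1, diluted: 0.72 v 0.54; SE = √(0.45/30) = 0.1225; 0.18/0.1225 = 1.470; 43%. Separated: n = 27; SE = 0.1217; ratio 1.643; 50%.
- q = 0.2, diluted: 0.64 v 0.48; SE = √(0.48/30) = 0.1265; 0.16/0.1265 = 1.265; 35%. Separated: n = 24; SE = 0.1291; ratio 1.549; 46%.
- q = 0.4, diluted: 0.48 v 0.36; SE = 0.1265; 0.12/0.1265 = 0.949; 24%. Separated: n = 18; SE = 0.1491; ratio 1.342; 38%.

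| Short-stay share | Difference (points) | Power, all men | Power, short-stay men separated |
|---|---|---|---|
| 0% | 20 | 53% | 53% |
| 10% | 18 | 43% | 50% |
| 20% | 16 | 35% | 46% |
| 40% | 12 | 24% | 38% |

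Using the pooled variance under the null instead gives 52% at q = 0, then 42%, 34% and 24% for all men and 48%, 45% and 37% separated. The pattern is the same.

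**Does the SAP's facility term do this job already?** A simulation (5,000 trials per scenario, Mantel-Haenszel test, same assumed rates) gave this power:

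| Short stays at the two sites | Unadjusted | Stratified by facility | Stratified by short stay |
|---|---|---|---|
| 20% at both | 0.325 | 0.330 | 0.445 |
| 0% and 60% | 0.275 | 0.323 | 0.412 |

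Facility recovers little when short stays are equally common at both sites, and only part of the loss when they cluster at one.

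**False positives.** With no treatment effect, rejection rates across all scenarios and all three analyses were 0.087 to 0.105, against a nominal 0.10.

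**The case against.** The strongest reply is that completion is undefined. A reader might infer that every man with under 12 weeks left fails by calendar. The documents do not say so. Completion could mean sessions attended, or staying to the planned discharge date. If reaching that date counts as completion, nothing is mixed and the loss is zero. This stands, and it makes the finding conditional.

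Second, flyers are handed out at intake, and on a 6-month stay a man must be randomized some 14 weeks after arrival to fall short. Short stays may be rare, and no document supports 20% or 40%. This stands too, and the shares above are scenarios. But no criterion closes the gap, and the protocol's own 12-week discharge does not fit a 6-month stay counted from intake.

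Third, a reader might infer that facility is ignored or left off an urn list. There is no list, only two classes, and the SAP already codes facility in its analyses. Balancing the urn on facility is therefore secondary.

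Fourth, a reader might infer bias, or expect adjustment to lift power above 53%. Neither is supported. Randomization protects the comparison, the simulated error rate stays near .10, and under this mechanism separating short-stay men recovers only part of what was lost.

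**Conclusion.** The point holds in conditional form. Time left in residence is derivable before randomization and bears on the residential part of hypothesis 1, and the plan does not use it. If short-stay men exist and count as non-completers, the plan gives up roughly 7, 11 or 14 points of recoverable power at short-stay shares of 10%, 20% or 40% (50 − 43, 46 − 35, 38 − 24), and the completion rates are harder to read as retention.

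This rests on equal arms, two-sided .10, completion of 80% v 60%, the assumed short-stay shares, and the recorded discharge date being the planned one. The loss is near nil with enrollment at intake, or if scheduled discharge is classed as completion. The effect is on power and interpretation only.

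**What to change.** 1. Define completion for hypothesis 1, state how a scheduled discharge before week 12 is classified, and reconcile the 12-week discharge with the 6-month stay.
2. Derive planned weeks left (recorded discharge date minus randomization date), report it by arm, and prespecify it as a covariate beside facility in the hypothesis 1 models. State its form, since a straight line will not capture a step at 12 weeks. If an under-12-weeks indicator causes separation, which it would if all such men are non-completers, use stratification or a penalized or exact method.
3. As a sensitivity analysis, report hypothesis 1 in men with at least 12 planned weeks left. This group is fixed before randomization, so the comparison stays randomized.
4. If allocation is still open, add facility as an urn factor. The SAP is written in the past tense, so this may no longer apply. If the analyses have already been run, label items 2 and 3 as added afterwards.

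The cost is one derived variable and a short SAP addition, with no new data collection. The downsides are one more model parameter and a smaller sample in the sensitivity analysis.

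### The SAP does not say whether the urn-balancing variables enter any model; for continuous outcomes compared on level at the end of the study, omitting them makes the test conservative

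*Protocol*

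**What the plan says.** **Allocation.** Under Study Design, the protocol says that "subjects will be assigned to treatment conditions through urn randomization using a Microsoft Access-based program". The stated purpose is "To increase the likelihood that treatment groups are balanced with respect to demographic variables, and moderators". It gives no list of urn variables, no cut-points and no urn parameters. Table 1 has a block of measures headed as moderators, several taken at baseline (childhood trauma, psychopathy, symptom inventory, addiction severity), but the protocol does not say which of them feed the urn.

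**Analysis.** The SAP's one general statement on design variables is "Across statistical analyses, dummy coding was used to represent facility and treatment assignment". It splits the outcomes in two:

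- Generalized linear models are used for process outcomes and for "secondary outcomes only measured once or twice at the end of treatment or the end of the 3-month period of follow-up".
- GEE is used for "between-group differences in the rate of change for primary and secondary outcomes measured two to five times from randomization". With three or more measurements, "time was coded as a continuous variable representing weeks from randomization"; with two, time is dummy coded.

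No urn variable or other baseline covariate is named, and none is ruled out. The significance threshold is .10, which the SAP justifies by the small sample and the cost of a Type II error. The planned sample is 60 fathers, with no power calculation.

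**Outcomes in the first group.** In Table 1, father-child free play is measured at 24 weeks only, client satisfaction at 16 weeks only, and the father engagement and contact scales at 16 and 24 weeks. None of these has a baseline value.

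**The concern.** An urn that reacts to baseline variables removes part of the chance imbalance on them. A linear model that omits those variables leaves their contribution in the residual variance, and so counts as random an imbalance that the design has already reduced. If the variables predict the outcome, the reported standard error exceeds the true sampling variability and the test rejects less often than its nominal level. Here the sponsor has deliberately relaxed that level to .10 to protect power, so a test that delivers less than .10 works against the stated aim. The missing information should be at hand, since the variables had to be specified for the urn program to run.

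**Working it through.** **Inputs.** From the documents: N = 60 and a threshold of .10. Assumed, because the documents do not give them: 1:1 allocation (30 per arm), a two-sided test, the number of urn factors, the urn rule, the effect size d, and R², the share of outcome variance that the urn factors explain. The plan has no power figure to reproduce. For orientation, 80% power at two-sided .10 corresponds to d = (1.645 + 0.842) × √(2/30) = 0.64.

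**Formula limits, continuous single-occasion outcome.** If balance on the factors were perfect, the unadjusted standard error would be too large by 1/√(1 − R²). The true type I error would then be 2 × [1 − Φ(1.645/√(1 − R²))]. Adjusted power is about Φ(d√15/√(1 − R²) − 1.645), with 0.65 × √15 = 2.517.

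| R² | SE ratio, perfect balance | Type I error, perfect balance | Adjusted power, d = 0.65 |
|---|---|---|---|
| 0 | 1.000 | .100 | 80.9% |
| 10% | 1.054 | .083 | 84.3% |
| 20% | 1.118 | .066 | 87.9% |
| 40% | 1.291 | .034 | 94.6% |

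An urn balances only partly, so the actual type I error should lie between the third column and .10.

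**Simulation, three binary factors, d = 0.65.** The range covers three separate sets of runs of a linear model with and without the urn factors. With 4,000 trials per cell, the Monte Carlo error at .10 is √(.1 × .9/4000) = .005.

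| R² | Type I error, unadjusted | Power, unadjusted | Power, adjusted | Gap in points |
|---|---|---|---|---|
| 10% | .090–.094 | 79–81% | 82–83% | 2–3 |
| 20% | .082–.088 | 81–82% | 86% | 4–5 |
| 40% | .062–.067 | 82–83% | 93% | 10–11 |

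Adjusted type I error was .098 to .102. At R² = 0, power was 79.6% unadjusted and 78.6% adjusted.

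**Four factors, d = 0.5.** The pattern is the same. Mean model SE divided by the true SD of the estimate was about 1.00, 1.00–1.03, 1.07 and 1.13–1.15 at R² = 0, .1, .3 and .5. Unadjusted type I error at the last three values was .088, .081 and .062. Power, unadjusted against adjusted, was 59.4 v 58.1%, 59.0 v 60.9%, 60.8 v 71.9% and 60.7 v 84.1%.

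**How much is due to the urn.** With three factors, R² = 40% and plain permuted allocation in place of the urn, power was 81.3% unadjusted and 93.1% adjusted. With the urn it was 82.1% and 93.2%. The gap is 11.8 points without the urn and 11.1 with it, so nearly all of it is the usual gain from adjustment. What the urn adds is the mismatch between the model's standard error and the true one.

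**Group-by-time contrast.** This was simulated as baseline-to-follow-up change, with four factors that act on level only. The SE ratio was 0.98–1.02 and unadjusted type I error .098–.105. Power was about 60% unadjusted and 58–59% adjusted at every R². The factors cancel within person.

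**Dichotomous outcome.** This was a logistic model with four strong factors, a conditional log odds ratio of 1.2 and 1,500 runs. Omission makes the median standard error smaller (0.550 against 0.674) and attenuates the mean estimate to 1.06. Power was 60.5% unadjusted and 66.0% adjusted, with type I error .090 and .115. Over the three null settings run, adjusted type I error was .113, .115 and .115. The mean is .114 over 4,500 runs, or (.114 − .100)/√(.1 × .9/4500) = .014/.0045, about 3 Monte Carlo errors above .10. Part of the apparent gain is therefore not real. Count and multinomial outcomes were not simulated.

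**The case against.** The strongest reply has four parts.

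1. The SAP clause describes how two variables are coded. It is not a closed list of terms. A reader might infer that the models contain nothing but facility and treatment, but the text does not say so: the GEE models also carry time and the between-group difference in rate of change, and on other covariates the SAP is silent. This stands, and the point is therefore one of omission.
2. A reader might infer that standard errors are too wide in every model, the primary outcomes included. The documents do not support that. The SAP tests repeatedly measured primary and secondary outcomes on rate of change, where factors acting on level alone do no harm. A loss would need factors that also predict change. That is conceivable for variables called moderators, but nothing in the documents establishes it. For dichotomous outcomes the effect on the standard error runs the other way.
3. The power gap mostly reflects a general preference for covariate adjustment. This also stands. The urn-specific part is the type I error below its nominal level.
4. R², d and the number of factors are assumptions, and facility, already modelled, may itself be an urn variable. This is true, and it is why a range that includes no loss is given.

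None of this answers the narrower point. Outcomes with no baseline measure get no protection from within-person cancellation when the arms are compared on level, and for the continuous ones the planned error bars are too wide if the urn variables are prognostic.

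**Conclusion.** The point holds for continuous outcomes compared between arms on level at the end of treatment or follow-up. In that setting, omitting prognostic urn variables gives a test that runs below its stated .10: about .09 if they explain 10% of outcome variance, .08 to .09 at 20%, and .06 to .07 at 40%. Power for d = 0.65 is about 2, 5 and 11 points below an adjusted analysis; with no explained variance there is nothing to recover. These sizes rest on three binary factors, an assumed urn rule, 30 per arm and two-sided testing.

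The error is conservative: it does not create false positives in these linear comparisons. It is not shown to affect the rate-of-change tests, and so does not by itself undermine the primary outcomes. The SAP's silence on the urn variables is still worth correcting, because a reader cannot tell whether the analysis follows the allocation scheme.

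**What to change.** In the SAP, list the variables programmed into the urn, with their categories, and say whether facility was one of them. Include those variables, in the form the urn used, as baseline covariates alongside facility in the generalized linear models for continuous end-of-study outcomes. For dichotomous, count and multinomial outcomes, report the adjusted model as a sensitivity analysis only, because adjusted logistic tests were slightly liberal at this sample size.

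The cost is a short addition to the SAP and a few degrees of freedom, more if the urn used many variables; with factors that predict nothing it is about 1 point of power. The SAP is written in the past tense, so the analysis may already be done. If so, the adjusted results should be labelled as added later.
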